Treatment Test product, dose and mode of administration Duration of treatment	
TG02 can be started on the day of enrollment.
 
Group A:
 
Patients with MGMT promoter-unmethylated tumors will receive TG02 (initial dose of 100 mg) orally twice weekly (days 1, 4, 8, 11, 15 and 18) in combination with standard involved-field hypofractionated RT (40 Gy in 15 fractions of 2.66 Gy) for 3 weeks (days 1-21). TG02 should be taken approximately one hour prior to RT.
 
Seven days after completing combination therapy, patients will receive maintenance cycles of single agent TG02 until disease progression, unacceptable toxicity or up to 12 months. TG02 will be administered on days 1, 4, 8, 11, 15, 18, 22 and 25 of each 28-day maintenance cycle. [Upon completion of 12 cycles without disease progression or unacceptable toxicity, patients may continue on TG02 as determined by the Investigator.]
 
Group B:
 
Patients with MGMT promoter-methylated tumors will receive TG02 (initial dose of 100 mg) orally twice weekly with temozolamide. TG02 will be taken on days -7, -4, 1, 4, 22 and 25 in cycle 1. As of cycle 2, TG02 is given on days 1, 4, 22 and 25 of a 28-day cycle. TMZ will be given in the standard 28-day cycle regimen (200 mg/m²) for 5 days q 28 starting at Day 1. Combination therapy will continue until disease progression, unacceptable toxicity or up to 12 cycles. [Upon completion of 12 cycles without disease progression or

	
unacceptable toxicity, patients may continue on TG02 and TMZ or single agent TG02 as determined by the Investigator.]
 
Group C:
 
Patients will receive single agent TG02 at 150 mg orally twice weekly. TG02 will be administered on days 1, 4, 8, 11, 15, 18, 22 and 25. The lowest permitted dose will be 100 mg BIW Single agent therapy will continue until disease progression, unacceptable toxicity or up to 12 cycles. [Upon completion of 12 cycles without disease progression or unacceptable toxicity, patients may continue on TG02 and TMZ or single agent TG02 as determined by the Investigator.]

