5.5.3 TG02

5.5.3.1 For all groups

The following dose levels of TG02 will/can be used:

- 150 mg (groups A,B,C)
- 100 mg (groups A,B, C)

TG02 dose should not be reduced below 100 mg. If a patient's initial or current dose is 100 mg and the patient experiences a toxicity requiring TG02 dose reduction as described in the tables below, the patient should be discontinued from study treatment.

TG02 should not be skipped for more than 28 days. If TG02 cannot be re-introduced within 28 days, the patient should be discontinued from the study treatment.

In case of uncertainty regarding dose modifications described in the tables below, please contact the Sponsor.

In all cases, appropriate symptomatic treatment should be considered to manage the AE.

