Grade 3 nausea Grade 3 or 4 vomiting	Skip one or more doses of TG02 until improved to grade ≤ 1 . If improved to grade ≤ 1 in <48 hours, re-introduce TG02 at the initial dose. If not improved to grade ≤ 1 with maximal supportive measures within 48 hours, re-introduce TG02 at a reduced dose *. Continue prophylaxis and management with at least moderate anti-emetic treatment (see Section 5.6.2).
Diarrhea	
Grade 1 or 2 event	Manage with anti-diarrheal treatment until improved to grade ≤ 1 . Prophylaxis should be given before TG02 dosing (see Section 5.6.2). If a patient experiences persistent or recurrent grade 2 diarrhea that does not improve to grade ≤ 1 with maximal supportive measures within 3 days, then TG02 dosing should be skipped until improved to grade ≤ 1 . The dose of TG02 may be reduced *. Continue prophylaxis and management with anti-diarrheal treatment (see Section 5.6.2).

Adverse Event	Action to be taken with TG02
Grade 3 or 4 event	
Skip one or more doses of TG02 until improved to grade ≤ 1. Physician should instruct patient regarding hydration. If improved to grade ≤ 1 in <48 hours, re-introduce TG02 at the initial dose.
 
If not improved to grade ≤ 1 with maximal supportive measures within 48 hours, re-introduce TG02 at a reduced dose *.
 
Continue prophylaxis and management with anti-diarrheal treatment (see Section 5.6.2)

Other non-hematologic events except alopecia and asymptomatic or reversible laboratory abnormalities	
First occurrence of grade 3 event	Skip one or more doses of TG02 until improved to grade ≤ 1 . Provide appropriate symptomatic treatment. Re-introduce TG02 at initial dose.
Second occurrence of the same grade 3 event	
Skip one or more doses of TG02 until improved to grade ≤ 1. Provide appropriate symptomatic treatment. Re-introduce TG02 at a reduced dose *.
 
If TG02 has been re-introduced after a second event and the event recurs, consider the individual benefit versus the risk of continuing TG02. If TG02 is re-introduced, re-introduce TG02 at a reduced dose *.
 
If TG02 has been re-introduced after a third event and the event recurs, discontinue TG02.

First occurrence of the same grade 4 event	Skip one or more doses of TG02 until improved to grade ≤ 1 . Provide appropriate symptomatic treatment. Re-introduce TG02 at a reduced dose*.

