5.5.3.3.3 TG02 or TMZ Hematological Adverse Events

The actions to be taken with TG02 or TMZ for hematological AEs in this study are based on these adverse event profiles. Hematological AEs should be managed as outlined in the table below and per local practice, where noted.

NOTE: * in below tables: There will be no dose reductions below 100 mg BIW

Group B: TG02-related Hematological Adverse Events

Adverse Event	Action to be taken with TG02/ TMZ
Thrombocytopenia	
Administration of TMZ or TG02 may induce thrombocytopenia. The profile of thrombocytopenia is different between TMZ and TG02. For TMZ, a nadir occurs around day 21. In a Phase 1b study of TG02 in combination with carfilzomib in multiple myeloma patients, 21% of patients administered TG02 at 250 mg bi-weekly experienced grade 3 or 4 thrombocytopenia. Onset was typically within the first week of administration and resolved within 72 hours after TG02 interruption. Attributing hematological and biochemical toxicity to TMZ versus TG02 may be challenging, This remains to be judged by the investigator, but guidance will be provided by the study chairs and Sponsor on an individual case-by-case basis.	
First occurrence of grade 3 event without bleeding	Skip one or more doses of TG02 and interrupt TMZ until improved to grade ≤1. Re-introduce TG02 and TMZ at initial dose.

Adverse Event	Action to be taken with TG02/ TMZ
Recurrence of the same grade 3 event without bleeding	
Skip one or more doses of TG02 and interrupt TMZ until improved to grade ≤ 1. Re-introduce TG02 at a reduced dose * and TMZ at a reduced dose.
 
If TG02/TMZ have been re-introduced after a second event and the event recurs, consider the individual benefit versus the risk of continuing TG02 or TMZ:
 
 • Discontinue TMZ. Continue TG02 at the same or a reduced dose * bi-weekly (on Days 1, 4, 8, 11, 15, 18, 22, 25) of a 28-day schedule. • Alternatively, discontinue TG02 and continue TMZ at a reduced dose 
If TG02 or TMZ has been re-introduced after a third event and the event recurs, discontinue TG02 and TMZ.

First occurrence of grade 3 with bleeding or grade 4 event occurring on Day -7 to Day -1 prior to Cycle 1 Day 1	
Skip one or more doses of TG02 until improved to grade ≤ 1. If improved to grade ≤ 1 by Cycle 1 Day 1, initiate TMZ at initial dose and re-introduce TG02 at a reduced dose *.

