Second occurrence of grade 3 event with bleeding or grade 4 event occurring on Day -7 to Day -1 of cycle	
Skip one or more doses of TG02 until improved to grade ≤ 1. If improved to grade ≤ 1 by Cycle 1 Day 1, initiate TMZ at initial dose. Consider the individual benefit versus the risk of continuing TG02. If TG02 is re-introduced, re-introduce at a reduced dose *.
 
If TG02 has been re-introduced after a third event and the event recurs, discontinue TG02.

First occurrence of grade 3 event with bleeding or grade 4 event occurring on Day 1 to Day 7 of cycle	
Skip one or more doses of TG02 and interrupt TMZ until improved to grade ≤ 1. Consider the individual benefit versus the risk of continuing TMZ:
 
 • If TMZ is re-introduced, re-introduce TMZ and TG02 at a reduced dose *. • If TMZ is discontinued, continue TG02 at the same or a reduced dose * bi-weekly (on Days 1, 4, 8, 11, 15, 18, 22, 25) of a 28-day schedule.
Second occurrence of grade 3 event with bleeding or grade 4 event occurring on day 1 to Day 7 of cycle	
Skip one or more doses of TG02 and interrupt TMZ (if TMZ was re-introduced after the first event) until improved to grade ≤ 1. Re-introduce TG02 at a reduced dose *. Discontinue TMZ.
 
If TG02 has been re-introduced after a second event and the event recurs, consider the individual benefit versus the risk of continuing TG02. If TG02 is re-introduced, re-introduce at a reduced dose *.
 
If TG02 has been re-introduced after a third event and the event recurs, discontinue TG02.

Adverse Event	Action to be taken with TG02/ TMZ
Grade 3 or 4 event occurring on Day 21 – Day 28 of cycle	Skip one or more doses of TG02 and TMZ until improved to grade ≤ 1 . Re-introduce TG02 at initial dose and re-introduce TMZ at a reduced dose.
Recurrent grade 4 event occurring on Day 21 – Day 28 of cycle	Discontinue TMZ. Consider the individual benefit versus the risk of continuing TG02. If TG02 is continued, continue TG02 at the same or a reduced dose * bi-weekly (on Days 1, 4, 8, 11, 15, 18, 22, 25) of a 28-day schedule. Alternatively, discontinue TG02 and rechallenge with TMZ at lower dose.
Grade 3 or 4 event that does not improve to grade ≤ 2 within 28 days	Discontinue patient from study.
Anemia (TMZ decision as per local practice)	
First occurrence of grade 3 event	Skip one or more doses of TG02 until improved to grade ≤ 2 . Re-introduce TG02 at initial dose.

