≥ 2 out of 3 or 6	
Dose escalation is stopped. If it occurs at 100 mg then trial is stopped without MTD. If it occurs at 150 mg then 100 mg is considered the MTD and as the recommended dose for phase II.
 
The safety at the MTD will also be assessed in additional patients up to a maximum of 24 patients in group A and 12 patients in group B. These totals include all patients recruited in the 3+3 escalation phase.

1 out of 3	
Enroll at least 3 more patients at this dose level.
 
If 0 of these 3 patients experience DLT, proceed to the next dose level up to a maximum TG02 dose of 150 mg. If it occurs at 150 mg then 150 mg is considered the MTD and as the recommended dose for phase II.
 
If 1 or more of this Group experience DLT, then dose escalation is stopped. If it occurs at 100 mg then trial is stopped without MTD. If it occurs at 150 mg then 100 mg is considered the MTD and as the recommended dose for phase II.
 
The safety at the MTD will also be assessed in additional patients up to a maximum of 24 patients in group A and 12 patients in group B. These totals include all patients recruited in the 3+3 escalation phase.

DLT = dose limiting toxicity

MTD = maximum tolerated dose

The MTD corresponds to the highest dose at which not more than 1 patient out of a maximum of 6 experiences a DLT. A compliance of 75% for TG02 and either RT (Group A) or TMZ (Group B) is required to assess the toxicity.

Group C

Further to the IDMC recommendations, the initial dose of TG02 was reduced from 200 to 150 mg with potential to escalate to 200 mg in case the first full cycle was well tolerated. During the follow-up IDMC meeting, the IDMC recommended to stop escalation to 200 mg. The initial statistical design remains applicable to eligible patients treated at initial dose of 150 mg.

Data collected at initial dose 200 mg (n=18) and 250 mg (n=6) will be analyzed for descriptive purpose only i.e., will not be included in the analysis below (primary analysis.)

Based on an A'Hern one-stage design, 45 eligible patients who started treatment will be evaluated for PFS at 6 months. It is estimated that the total sample size should not be larger than 50 assuming a dropout of 10%.

The following hypotheses apply:

- P_0 is the largest PFS rate at 6 months which, if true, implies that the therapeutic activity of TG02 is too low. In the present trial, P_0 has been taken as 20%.

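### Sixteen toxicity-table rows restart TG02 at the initial dose without providing for a patient already cut from 150 to 100 mg; read literally, they return that patient to 150 mg

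*Combined protocol and SAP*

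**What the plan says.** Section 5.5.3.1 allows two TG02 dose levels, 150 mg and 100 mg, with no reduction below 100 mg. A patient whose "initial or current dose is 100 mg and the patient experiences a toxicity requiring TG02 dose reduction" is to be discontinued from study treatment. The same section adds: "In case of uncertainty regarding dose modifications described in the tables below, please contact the Sponsor".

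The tables for each group then set the action by event. Five kinds of event restart TG02 at the initial dose in all three groups:

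- a first grade 3 thrombocytopenia without bleeding
- a first grade 3 anemia
- grade 3 nausea or grade 3-4 vomiting that settles within 48 hours
- grade 3-4 diarrhea that settles within 48 hours (in Group A, "in <48 hours, re-introduce TG02 at the initial dose")
- a first grade 3 event among the other non-hematologic toxicities

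Group B has a sixth such row, for grade 3 or 4 thrombocytopenia on Days 21-28: "Re-introduce TG02 at initial dose and re-introduce TMZ at a reduced dose".

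The asterisk in the tables marks only the 100 mg floor. Nothing in section 5.5 says that a dose, once reduced, stays reduced.

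**The concern.** A patient who starts at 150 mg can be cut to 100 mg for one toxicity and later meet a row that prescribes the initial dose. A site that follows the row as written answers a further severe drug-related event with a higher dose and undoes an earlier safety reduction. A site that takes *initial* to mean the dose just before the event keeps 100 mg. Two patients with the same history could therefore be dosed differently.

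The earlier reduction may well have been for neutropenia, which requires one at the first grade 3 event in all three groups. After cycle 1, scheduled blood counts fall only once per 28-day cycle (sections 6.2.4.1 and 7.3.2), so the schedule alone would not catch a renewed fall in neutrophils early.

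**Working it through.** **1. Count of rows that restart TG02 at the initial dose.** Rows in which only TMZ returns at its initial dose are left out.

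| Row type | A | B | C | Total |
|---|---|---|---|---|
| First grade 3 (thrombocytopenia without bleeding, anemia, other non-hematologic) | 3 | 3 | 3 | 9 |
| Nausea/vomiting and diarrhea settling in <48 h | 2 | 2 | 2 | 6 |
| Thrombocytopenia grade 3-4, Days 21-28 | 0 | 1 | 0 | 1 |
| Total | 5 | 6 | 5 | 16 |

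**2. What the term means.** Section 5.5.3.1 sets a patient's initial dose beside the current dose as alternatives, so within the dose-modification rules they are not synonyms. For Group C, section 8.1.1 uses the term for the starting dose: "The initial statistical design remains applicable to eligible patients treated at initial dose of 150 mg". Read this way, the initial dose of a 150 mg starter remains 150 mg after a cut.

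**3. A path through the tables.** A Group C patient starts at 150 mg. Grade 3 neutropenia requires a reduction, so TG02 resumes at 100 mg. Later the patient has grade 3-4 diarrhea that improves to grade 1 or less in under 48 hours. The diarrhea row in section 5.5.3.4 restarts TG02 at the initial dose, which is 150 mg.

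**4. Which rows can do this.**

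- After a cut for a different type of event, all 16 rows can.
- After a cut for the same toxicity, the six nausea/vomiting and diarrhea rows clearly can, because they have no first-occurrence limit.
- The Group B Days 21-28 row can do so only in an unusual sequence, such as a grade 4 event on Days 1-7 that reduced TG02 followed by a grade 3 event on Days 21-28. That row does not itself reduce TG02, and neighbouring rows deal with recurrences.

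**5. The two branches of the six rows, for a patient now on 100 mg.** Settling in under 48 hours gives the initial dose, 150 mg. Taking longer requires a reduction, which at 100 mg means discontinuation under section 5.5.3.1. No branch leaves the patient on 100 mg.

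**6. Size of the dose change.**

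- Per dose: 150/100 = 1.5, i.e. +50%.
- Eight doses per 28-day cycle (Group C, Group A maintenance): 8 × 150 = 1200 mg against 8 × 100 = 800 mg.
- Four doses per cycle (Group B, cycle 2 onwards): 4 × 150 = 600 mg against 4 × 100 = 400 mg.

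**7. Who could be exposed.** Only patients who start at 150 mg. The planning totals in section 8.1.1 give about 50 in Group C. In Groups A and B the totals include the escalation patients, of whom at least 3 per group start at 100 mg, which leaves 24 − 3 = 21 evaluable in Group A and 12 − 3 = 9 in Group B. Of these, only patients first reduced and then meeting one of the 16 rows are affected. The documents give no rate for that sequence.

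**The case against.** The best answer is that nobody meant doses to go back up. Sections 5.2.1.1 and 5.2.1.2 keep Group A and B patients without a cycle 1 DLT on the same TG02 dose, and the only departures they name are a reduction or a delay. The introductions to the tables (5.5.3.2.1, 5.5.3.2.2, 5.5.3.3.1, 5.5.3.3.2 and 5.5.3.4) speak only of reductions and skipped doses for TG02. In Group C, planned escalation to 200 mg was stopped on IDMC advice (section 8.1.1); that concerned a higher dose, but it points the same way. This stands as evidence of intent. A reader might infer that the protocol deliberately orders re-escalation, and the documents do not support that.

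The nine first-occurrence rows can also be read as a ladder for each toxicity, in which a first event restarts at the initial dose and a recurrence at a lower one. In Group B, for example, the recurrence of grade 3 thrombocytopenia without bleeding has "Re-introduce TG02 at a reduced dose * and TMZ at a reduced dose". The authors may simply have assumed no earlier cut. That explains the wording but does not cover the patient who was cut for something else, and the six gastrointestinal rows have no such ladder.

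Two pieces of support for the literal reading are weaker than they look. The protocol summary says that Group A patients "will receive TG02 (initial dose of 100 mg) orally twice weekly", and the same figure appears for Group B. A reader might take this as a definition of each patient's initial dose, but it is the first cohort level and settles nothing for an individual who starts at 150 mg. Seven Group B entries use the formula "Continue TG02 at the same or a reduced dose", which shows that other wording was available. All seven, however, deal with TG02 once TMZ is stopped, so the contrast is suggestive only.

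Finally, uncertain sites are told to contact the sponsor. That helps a site that notices the ambiguity; a site applying the row as written has no prompt to call.

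**Conclusion.** The point holds as a flaw in a stated rule. For a patient who started at 150 mg and is on 100 mg, 16 rows give an instruction whose literal meaning is a 50% dose increase after a further grade 3-4 TG02-related event, and no sentence overrides it. This rests on reading *initial dose* as the patient's own starting dose, which section 5.5.3.1 supports for all groups and section 8.1.1 for Group C. Confidence is medium, because the intent was probably otherwise.

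The reach is limited. Few patients are likely to be affected, and their number cannot be derived. A reader might take 50, 21 and 9 as caps or as counts of affected patients. They are neither: the 50 is an estimate, the other two count evaluable patients only, and replaced patients may also start at 150 mg.

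A reader might also infer damage to the efficacy or safety analysis. The documents do not support that. The PFS-6 decision rule and the DLT rules are unchanged, and the adverse-event tables in section 8.2.2 take the worst grade per patient, not by current dose. The consequence is for patient safety and consistent conduct between sites, which is enough to warrant the correction.

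**What to change.** In the 16 rows, replace the initial dose with *the dose in force before the event*. For patients never reduced, and for those who started at 100 mg, nothing changes. For a reduced patient, the quick-recovery branch then keeps 100 mg, and the longer branch still leads to discontinuation as section 5.5.3.1 already requires. The cost is a wording change in the next amendment, with no added patients, visits or data; dose modifications already go on the CRF (section 7.1.1).

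Two further changes go beyond the defect and are for the sponsor to decide:

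- A sentence in section 5.5.3.1 that TG02 is not re-escalated once reduced. This is a new clinical rule, and its price is that reduced patients could not return to 150 mg.
- Matching wording in the three Group B entries that restart TMZ at its initial dose (first grade 3 thrombocytopenia without bleeding, first grade 3 neutropenia, first other grade 3 non-hematologic event). This would be for consistency only, since section 5.5.2 leaves TMZ changes largely to institutional practice.

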5.5.3.3 Group B

5.5.3.3.1 Dose escalation phase

Cycle 1: no TG02 or TMZ dose reductions are allowed in Cycle 1 except if a patient experiences a DLT.

Skipped doses of TG02 are allowed. A "skipped dose" for TG02 when TMZ is not interrupted means that one or more single doses will be omitted and not replaced, in order not to change the temporal relationship with TMZ.

For example, if TG02 is planned on days 1, 4 and 22, but day 4 has to be omitted, TG02 can be restarted on day 22 if the AE is sufficiently resolved: TG02 is always restarted on a scheduled dose day.

Interruptions of TMZ are allowed.

Skipping TG02 or interrupting TMZ for >25% of the planned total dose in Cycle 1 will be considered a DLT (see section 5.5.1).

Toxicities possibly related to TG02 should be managed as outlined in the tables below. Toxicities of TMZ should be managed as outlined in the table below and per local practice, where noted.

Cycles 2+: TG02 dose reductions and skipped dose(s) can be made for adverse events as described in the tables below. TMZ dose reductions and interruptions can be made for adverse events as described in section 5.5.2 and the tables below.

5.5.3.3.2 Expansion phase

TG02 dose reductions and skipped dose(s) are allowed in any cycle as described in the tables below. A "skipped dose" for TG02 when TMZ is not interrupted means that one or more single doses will be omitted and not replaced, in order not to change the temporal relationship with TMZ.

For example, if TG02 is planned on days 1, 4 and 22, but day 4 has to be omitted, TG02 can be restarted on day 22 if the AE is sufficiently resolved: TG02 is always restarted on a scheduled dose day.

Toxicities possibly related to TG02 should be managed as outlined in the tables below. Toxicities of TMZ should be managed as outlined in the table below and per local practice, where noted.

In the absence of progressive disease, either TMZ or TG02 may be interrupted/ skipped or discontinued permanently while treatment with the other agent is continued. In all cases where TMZ has to be discontinued, patient can continue with TG02. Otherwise patient is considered off study and treating physician can consider other treatment such as RT.

5.5.3.3.3 TG02 or TMZ Hematological Adverse Events

The actions to be taken with TG02 or TMZ for hematological AEs in this study are based on these adverse event profiles. Hematological AEs should be managed as outlined in the table below and per local practice, where noted.

NOTE: * in below tables: There will be no dose reductions below 100 mg BIW

Group B: TG02-related Hematological Adverse Events

Adverse Event	Action to be taken with TG02/ TMZ
Thrombocytopenia	
Administration of TMZ or TG02 may induce thrombocytopenia. The profile of thrombocytopenia is different between TMZ and TG02. For TMZ, a nadir occurs around day 21. In a Phase 1b study of TG02 in combination with carfilzomib in multiple myeloma patients, 21% of patients administered TG02 at 250 mg bi-weekly experienced grade 3 or 4 thrombocytopenia. Onset was typically within the first week of administration and resolved within 72 hours after TG02 interruption. Attributing hematological and biochemical toxicity to TMZ versus TG02 may be challenging, This remains to be judged by the investigator, but guidance will be provided by the study chairs and Sponsor on an individual case-by-case basis.	
First occurrence of grade 3 event without bleeding	Skip one or more doses of TG02 and interrupt TMZ until improved to grade ≤1. Re-introduce TG02 and TMZ at initial dose.

Adverse Event	Action to be taken with TG02/ TMZ
Recurrence of the same grade 3 event without bleeding	
Skip one or more doses of TG02 and interrupt TMZ until improved to grade ≤ 1. Re-introduce TG02 at a reduced dose * and TMZ at a reduced dose.
 
If TG02/TMZ have been re-introduced after a second event and the event recurs, consider the individual benefit versus the risk of continuing TG02 or TMZ:
 
 • Discontinue TMZ. Continue TG02 at the same or a reduced dose * bi-weekly (on Days 1, 4, 8, 11, 15, 18, 22, 25) of a 28-day schedule. • Alternatively, discontinue TG02 and continue TMZ at a reduced dose 
If TG02 or TMZ has been re-introduced after a third event and the event recurs, discontinue TG02 and TMZ.

First occurrence of grade 3 with bleeding or grade 4 event occurring on Day -7 to Day -1 prior to Cycle 1 Day 1	
Skip one or more doses of TG02 until improved to grade ≤ 1. If improved to grade ≤ 1 by Cycle 1 Day 1, initiate TMZ at initial dose and re-introduce TG02 at a reduced dose *.

Second occurrence of grade 3 event with bleeding or grade 4 event occurring on Day -7 to Day -1 of cycle	
Skip one or more doses of TG02 until improved to grade ≤ 1. If improved to grade ≤ 1 by Cycle 1 Day 1, initiate TMZ at initial dose. Consider the individual benefit versus the risk of continuing TG02. If TG02 is re-introduced, re-introduce at a reduced dose *.
 
If TG02 has been re-introduced after a third event and the event recurs, discontinue TG02.

First occurrence of grade 3 event with bleeding or grade 4 event occurring on Day 1 to Day 7 of cycle	
Skip one or more doses of TG02 and interrupt TMZ until improved to grade ≤ 1. Consider the individual benefit versus the risk of continuing TMZ:
 
 • If TMZ is re-introduced, re-introduce TMZ and TG02 at a reduced dose *. • If TMZ is discontinued, continue TG02 at the same or a reduced dose * bi-weekly (on Days 1, 4, 8, 11, 15, 18, 22, 25) of a 28-day schedule.
Second occurrence of grade 3 event with bleeding or grade 4 event occurring on day 1 to Day 7 of cycle	
Skip one or more doses of TG02 and interrupt TMZ (if TMZ was re-introduced after the first event) until improved to grade ≤ 1. Re-introduce TG02 at a reduced dose *. Discontinue TMZ.
 
If TG02 has been re-introduced after a second event and the event recurs, consider the individual benefit versus the risk of continuing TG02. If TG02 is re-introduced, re-introduce at a reduced dose *.
 
If TG02 has been re-introduced after a third event and the event recurs, discontinue TG02.

Adverse Event	Action to be taken with TG02/ TMZ
Grade 3 or 4 event occurring on Day 21 – Day 28 of cycle	Skip one or more doses of TG02 and TMZ until improved to grade ≤ 1 . Re-introduce TG02 at initial dose and re-introduce TMZ at a reduced dose.
Recurrent grade 4 event occurring on Day 21 – Day 28 of cycle	Discontinue TMZ. Consider the individual benefit versus the risk of continuing TG02. If TG02 is continued, continue TG02 at the same or a reduced dose * bi-weekly (on Days 1, 4, 8, 11, 15, 18, 22, 25) of a 28-day schedule. Alternatively, discontinue TG02 and rechallenge with TMZ at lower dose.
Grade 3 or 4 event that does not improve to grade ≤ 2 within 28 days	Discontinue patient from study.
Anemia (TMZ decision as per local practice)	
First occurrence of grade 3 event	Skip one or more doses of TG02 until improved to grade ≤ 2 . Re-introduce TG02 at initial dose.
Recurrence of the same grade 3 event	Skip one or more doses of TG02 until improved to grade ≤ 2 . Re-introduce TG02 at reduced dose *. If TG02 has been re-introduced after a second event and the event recurs, discontinue TG02.
Grade 4 event	Skip one or more doses of TG02 until improved to grade ≤ 1 . Consider the individual benefit versus the risk of continuing TG02 at reduced dose *. If TG02 is re-introduced, re-introduce at a reduced dose *.
Recurrence of the same grade 4 event	Discontinue TG02.
Neutropenia	
First occurrence of grade 3 event	Skip one or more doses of TG02 and interrupt TMZ until improved to grade ≤ 1 . Re-introduce TG02 at a reduced dose * and TMZ at initial dose.

Adverse Event	Action to be taken with TG02/ TMZ
Recurrence of the same grade 3 event	
Skip one or more doses of TG02 and interrupt TMZ until improved to grade ≤ 1. Re-introduce TG02 * and/ or TMZ at a reduced dose.
 
If TG02 and TMZ have been re-introduced after a second event and the event recurs, consider the individual benefit versus the risk of continuing TG02 or TMZ:
 
 • Discontinue TMZ. Continue TG02 at the same or a reduced dose *bi-weekly (on Days 1, 4, 8, 11, 15, 18, 22, 25) of a 28-day schedule. • Alternatively, discontinue TG02 and continue TMZ at a reduced dose. 
If TG02 or TMZ has been re-introduced after a second event and the event recurs, discontinue TG02 and TMZ.

Grade 4 event	Skip one or more doses of TG02 and TMZ until improved to grade ≤ 1 . Re-introduce TG02 * and TMZ at a reduced dose.
Recurrence of the same grade 4 event	Discontinue TG02. TMZ dosing as per local practice.
Febrile Neutropenia	
Grade 3 or 4 event	Skip one or more doses of TG02 and interrupt TMZ until fever is resolved and neutropenia is improved to grade ≤ 1 . Re-introduce TG02 * and TMZ at a reduced dose.
Recurrence of the same grade 3 event	
Skip one or more doses of TG02 and interrupt TMZ until fever is resolved and neutropenia is improved to grade ≤ 1. Consider the individual benefit versus the risk of continuing TG02 or TMZ:
 
 • Discontinue TMZ. Continue TG02 at the same or a reduced dose * bi-weekly (on Days 1, 4, 8, 11, 15, 18, 22, 25) of a 28-day schedule. • Alternatively, discontinue TG02 and continue TMZ at a reduced dose. 
If TG02 or TMZ has been re-introduced after a second event and the event recurs, discontinue TG02 and TMZ.

Recurrence of the same grade 4 event	Discontinue TG02 and TMZ.

Group B: TG02-related Non-hematologic Adverse Events

Adverse Event	Action to be taken with TG02
Nausea / Vomiting (TMZ decision as per local practice)	
Grade 1 or 2 event	
Manage with moderate anti-emetic treatment until improved to grade ≤ 1. Prophylaxis should be given before TG02 dosing (see Section 5.6.2).
 
If a patient experiences persistent or recurrent grade 2 nausea/vomiting that do not improve to grade ≤ 1 with maximal supportive measures within 3 days, then TG02 dosing should be skipped until improved to grade ≤ 1. The dose of TG02 may be reduced *.

Grade 3 nausea Grade 3 or 4 vomiting	
Skip one or more doses of TG02 until improved to grade ≤ 1. If improved to grade ≤ 1 in <48 hours, re-introduce TG02 at the initial dose.
 
If not improved to grade ≤ 1 with maximal supportive measures within 48 hours, re-introduce TG02 at a reduced dose *.
 
Continue prophylaxis and management with at least moderate anti-emetic treatment (see Section 5.6.2).

Diarrhea (TMZ decision as per local practice)	
Grade 1 or 2 event	
Manage with anti-diarrheal treatment until improved to grade ≤ 1. Prophylaxis should be given before TG02 dosing (see Section 5.6.2).
 
If a patient experiences persistent or recurrent grade 2 diarrhea that does not improve to grade ≤ 1 with maximal supportive measures within 3 days, then TG02 dosing should be skipped until improved to grade ≤ 1. The dose of TG02 may be reduced *.
 
Continue prophylaxis and management with anti-diarrheal treatment (see Section 5.6.2).

Grade 3 or 4 event	
Skip one or more doses of TG02 until improved to grade ≤ 1. Physician should instruct patient regarding hydration. If improved to grade ≤ 1 in <48 hours, re-introduce TG02 at initial dose.
 
If not improved to grade ≤ 1 with maximal supportive measures within 48 hours, re-introduce TG02 at a reduced dose *.
 
Continue prophylaxis and management with anti-diarrheal treatment (see Section 5.6.2).

Cardiotoxicity	
Grade 3 event	
Discontinue TMZ.
 
Consider the individual benefit versus risk of continuing TG02. If TG02 is continued, continue TG02 at the same or a reduced dose * bi-weekly (on Days 1, 4, 8, 11, 15, 18, 22, 25) of a 28-day schedule.

Adverse Event	Action to be taken with TG02
Hepatotoxicity	
First occurrence of grade 3 event	
Skip one or more doses of TG02 and interrupt TMZ until improved to grade ≤ 1. Re-introduce TG02 at a reduced dose *.
 
Consider the individual benefit versus the risk of continuing TMZ. If TMZ is re-introduced, re-introduce at a reduced dose.

Recurrence of the same grade 3 event	
If TMZ was re-introduced after the first event, discontinue TMZ. Skip one or more doses of TG02 until improved to grade ≤ 1. Consider the individual benefit versus the risk of continuing TG02. If TG02 is re-introduced, re-introduce at a reduced dose *.
 
If TG02 has been re-introduced after a second event and the event recurs, discontinue TG02.

First occurrence of grade 4 event	Discontinue TMZ. Skip one or more doses of TG02 until improved to grade ≤ 1 . Consider the individual benefit versus the risk of continuing TG02 at reduced dose *. If TG02 is re-introduced, re-introduce at a reduced dose *.
Recurrence of the same grade 4 event	Discontinue TG02.
Other non-hematologic events except alopecia and asymptomatic or reversible laboratory abnormalities	
First occurrence of grade 3 event	Skip one or more doses of TG02 and interrupt TMZ until improved to grade ≤ 1 . Provide appropriate symptomatic treatment. Re-introduce TG02 and TMZ at initial dose.
Second occurrence of the same grade 3 event	
Skip one or more doses of TG02 and interrupt TMZ until improved to grade ≤ 1. Provide appropriate symptomatic treatment. Re-introduce TG02 * and TMZ at a reduced dose.
 
If TG02 and TMZ have been re-introduced after a second event and the event recurs, discontinue TG02 and/ or TMZ.

First occurrence of the same grade 4 event	Skip one or more doses of TG02 and interrupt TMZ until improved to grade ≤ 1 . Provide appropriate symptomatic treatment. Re-introduce TG02 * and TMZ at a reduced dose.
Second occurrence of the same grade 4 event	
Skip one or more doses of TG02 and interrupt TMZ until improved to grade ≤ 1. Provide appropriate symptomatic treatment. Consider the individual benefit versus the risk of continuing TG02 and TMZ:
 
 • Discontinue TMZ. Continue TG02 at the same or a reduced dose * bi-weekly (on Days 1, 4, 8, 11, 15, 18, 22, 25) of a 28-day schedule. • Alternatively, discontinue TG02 and continue TMZ at a reduced dose.

